##### Rationale for Sample Size:

There are no previous studies that have specifically examined the impact of inhalation management education on sleep quality. In prior studies, the mean PSQI (Pittsburgh Sleep Quality Index) scores among patients with COPD ranged from 8.3 to 11.5, with a commonly used cutoff score of 5.5 to indicate poor sleep quality. Based on this, we assumed a mean reduction of 5.0 points in the PSQI-J score at 3 months in the intervention group.

Using a two-tailed test with a significance level of 5% ( $\alpha = 0.05$ ) and a power of 80% ( $\beta = 0.20$ ), the required sample size was calculated to be 17 participants per group.

[figure not shown]
However, considering that many participants are older adults who may face challenges in consistently using personal computers or video conferencing tools, a higher dropout rate than usual is expected. Therefore, we increased the target enrollment to 30 participants per group, for a total of 60 participants.

#### 6. Research Outline

After obtaining research consent, baseline attributes, inhalation technique checks, and pre-intervention sleep assessments are conducted. For the pre-intervention assessment, a Watch Pad 200U or 300 is loaned to participants, who wear it overnight at home to record sleep onset.

After random assignment, the intervention group undergoes two inhalation technique

checks and inhalation management education sessions during an 8-week follow-up period. At the study's conclusion, participants undergo an inhalation technique check, sleep assessment, and questionnaire survey. If inhalation technique errors persist after training completion and the participant requests it, inhalation management education will be provided post-study. For the control group, these technique checks and education involve sending a pamphlet on using the same device as their prescribed inhaled medication at enrollment or approximately one week after enrollment, followed by an inhalation technique check via video conference. After a 12-week observation period, the study concludes with an inhalation technique check, sleep assessment, and questionnaire completion at the study end. Additionally, inhalation management education will be provided after the study concludes if the participant requests it.

## 7. Intervention

The intervention content for the education intervention group is described below. The usual care group will receive only the same pamphlet as the intervention group, without any explanation or instruction on inhalation techniques.

### First Intervention Session (within one month of participant enrollment):

- 1) During a video conference, the participant will be asked to use their prescribed inhaled medication while the study staff (applicant) observes their inhalation technique. The staff will assess the technique using a standardized technical checklist. Feedback will be provided based on the assessment, and any technical errors will be corrected through demonstration of the correct inhalation method.

- 2) Education will be provided on self-management, including how to use inhaled medications in response to symptoms such as dyspnea and cough perceived in daily life, appropriate timing of inhalation, and self-monitoring strategies.

**Second Intervention Session (four weeks after the first session):**

- 1) During a video conference, the participant will again demonstrate inhalation using their prescribed inhaler, observed by the study staff who will assess technique with the checklist. Feedback will be given, and any technical errors will be addressed through correct method demonstration.
- 2) The staff will inquire about any difficulties or symptoms experienced by the participant since the previous intervention, and discuss inhaler use and management strategies together with the participant.

**8. Evaluation Items****(1) Primary Evaluation Item**

Improvement in the Japanese version of the Pittsburgh Sleep Quality Index (PSQI-J)  
[Rationale]

The PSQI (Pittsburgh Sleep Quality Index) is a scale for evaluating sleep quality. It is the most widely used and standardized measure globally, employed in numerous clinical trials. A Japanese version, PSQI-J, has also been developed. Since this study aims to examine sleep quality improvement as an effect of inhalation management education, this scale was selected as the primary outcome measure.

The PSQI-J is a questionnaire assessing sleep status over the past month. It consists of 19 self-reported items and seven subscales: Sleep Quality, Sleep Onset, Sleep Duration, Sleep Efficiency, Sleep Difficulty, Sleep Medication Use, and Daytime Sleepiness. A total score ranging from 0 to 3 points (0–21 points total) is calculated, with higher scores indicating greater sleep impairment.

Assessment timepoints were at participant registration, the second intervention session, and study completion.

**(2) Secondary Evaluation Items****1) Sleep Quality**

① Japanese Version of Epworth Sleepiness Scale (JESS)  
[Rationale]

JESS is a scale used to assess subjective daytime sleepiness and diagnose sleep disorders. It has been modified with items tailored to Japanese lifestyles, and its reliability and validity in the Japanese population have been verified. Similar to PSQI-

J, since nighttime sleep conditions are thought to influence daytime sleepiness and related states, we will evaluate improvements in subjective symptoms using JESS. Assessment points are set at: before the first intervention, during the second intervention, and at the end of the observation period.

Respondents answer eight questions using a 4-point scale: “0 points” for “Very unlikely to doze off” and “3 points” for “Very likely to doze off.” A total score of 11 points or higher indicates a high likelihood of sleep apnea syndrome.

②Nighttime Sleep Assessment (AHI, ODI3%, ODI4%, average nighttime SpO2, time with nighttime SpO2 <90%, arousal status)

**【Rationale】**

Bronchodilator effects of 82 agonists, anticholinergic agents, and inhaled corticosteroids, along with improvements in nighttime SaO2 and AHI, have been reported. In this study, it is presumed that correct inhalation implementation enhances drug efficacy and further improves nocturnal sleep status. Therefore, these parameters were set as secondary endpoints for objective evaluation.

Watch PAT continuously measures peripheral arterial blood flow throughout the night and calculates AHI, ODI, nocturnal hypoxia, arousals, and REM sleep depth. In studies comparing Watch PAT to PSG, strong correlations were confirmed for AHI and RDI measurements ( $r=0.889$  [95% CI: 0.862-0.911];  $P<0.001$ ). Watch PAT enables objective sleep assessment without requiring measurements in non-routine settings like hospitals and without burdening subjects. Assessment points are at participant enrollment and at the end of the observation period.

③Japanese Version of CAT (COPD Assessment Test)

**【Rationale】**

The St George's Respiratory Questionnaire (SGRQ) is a respiratory disease-specific QOL measure developed for COPD patients. However, it contains 80 items and takes approximately 20 minutes to complete. In contrast, the CAT was developed as a shorter, simpler questionnaire to assess the impact of COPD on patients' lives. It shows good correlation with the SGRQ ( $r=0.80$ ,  $p<0.0001$ ). Furthermore, the Japanese version of the CAT, adapted to the Japanese lifestyle, also demonstrated high internal consistency (Cronbach's alpha: 0.891), a high correlation with the SGRQ ( $r \approx 0.82$ ,  $p<0.001$ ), and showed a correlation with the general health-related QOL questionnaire (SF-12v2). Therefore, this study will use the Japanese version of the CAT to assess patient QOL. The assessment points were set at the time of participant registration and at the end of the observation period, in accordance with the CAT Policy Committee and the GOLD Strategy Document.

The assessment uses an 8-item scale (cough, sputum production, breathlessness, dyspnea on exertion, daily activities, confidence in going out, sleep, and energy) rated on a 6-point scale from 0 to 5, with a total score out of 40. A higher total score indicates a worsening health status.

2) Items related to inhalation technique

① Number and content of technical errors assessed using the inhalation technique checklist

[Rationale]

To evaluate whether the intervention enabled patients to perform inhalation correctly using device-specific checklists. The inhalation technique checklists were developed based on prior research. Evaluation points are after the first intervention, before and after the second intervention, and at the end of the observation period.

## 9. Observation and Examination Items and Schedule

In this study, the following information will be collected from the participant at the time of enrollment, at the time of intervention, and at the end of the study, either through direct interview with the participant or by retrieving it from medical records with the participant's permission. Sleep evaluation will be measured for research purposes (research funding).

### At the time of enrollment

[Patient Basic Information]

Patient Background: Age, Gender, Smoking History, BMI, Disease Duration, Alcohol Consumption (presence/absence and frequency), Use of Sleep Medications, Hospitalization within the Past 6 Months, Presence of Comorbidities (e.g., Diabetes, Heart Disease, Stroke, Hypertension, Depression, Cognitive Impairment), mMRC, Types and Number of Inhaled Medications

Respiratory Function: FVC (ml), FEV1 (ml), FEV1/FVC (%), %FEV1 (%) measured between 6 months prior to enrollment and the first intervention

Sleep assessment: AHI, ODI, snoring level, wakefulness/sleep depth, REM sleep structure, oxygen saturation (mean minimum oxygen saturation, frequency of oxygen saturation drops, heart rate during sleep) using Watch Pad 200U or 300

Inhalation therapy experience: Presence/absence of inhalation therapy instruction and details (providing profession, time since last instruction, past instruction method [demonstration, video, pamphlet, verbal])

[Self-Administered Questionnaire I]

Anxiety/Depression Tendencies: Japanese Version of the Hospital Anxiety and Depression Scale (HADS)

QOL: Japanese Version of the CAT

Sleep Quality: PSQI-J, JESS

Initial Intervention: Within one month of participant registration

Inhalation Technique: Assessment using the Inhalation Technique Checklist

- Presence of technical errors

Second Intervention: Approximately 4 weeks after initial intervention

Inhalation Technique: Assessment using Inhalation Technique Checklist

- Presence of technical errors
- Changes to device, medication content, or frequency and reasons

[Self-Report Questionnaire II]

Sleep Quality: PSQI-J, JESS

Anxiety/Depression Tendencies: HADS

Study Completion (Approximately 8 weeks after second intervention)

Inhalation Technique: Assessment using Inhalation Technique Checklist

- Presence of technical errors
- Changes in device, medication type, or dosage frequency and their reasons

Sleep Assessment: AHI, ODI, snoring level, arousal/sleep depth, body position, REM sleep structure, oxygen saturation statistics (mean minimum oxygen saturation, frequency of oxygen saturation drops, heart rate during sleep) using Watch Pad 200U or 300

[Self-Report Questionnaire III]

Sleep Quality: PSQI-J, JESS

QOL: Japanese CAT

Anxiety/Depression Tendencies: HADS

Presence of unscheduled visits or hospitalizations from enrollment to study completion

[Brochure]

Self-assessment of inhaler usage, inhalation log (symptoms of breathlessness, cough/phlegm, self-rated sleep)

Table1. Inspection Schedule

	within 6weeks	registration	Initial intervention	Second intervention	At the completion of the research	Cancellation
Pulmonary Function Test	○					
Patient Basic Attributes		○				
QOL (Quality of life)		○		○	○	△
PSQI · JESS (Sleep quality)		○		○	○	△
Sleep Assessment (Sleep study)		○			○	△
Check of inhalation technique		○※	○※	○	○	△
HADS (Anxiety and Depressive Tendencies)		○		○	○	△
Unplanned medical visits or hospitalizations					○	△
Observation of adverse events			◀	▶		△
Inhalation Management Log					○	△

“○” indicates required items; “△” indicates optional items;

“※” indicates items to be completed during registration or around the time of the first intervention.

## 10. Analysis Methods

### 1) Analysis of Primary Endpoint

#### Primary Endpoint: PSQI-J at 3 months post-educational intervention

Analysis of the primary endpoint will be performed using the Full Analysis Set (FAS). The change in PSQI-J for each group will be calculated, and between-group comparisons will be performed at a 5% significance level (two-tailed) using covariance analysis adjusted for the background factors of age and disease stage classification. A similar analysis will be performed secondarily using PPS as the analysis population.

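### The primary analysis is a one-time-point ANCOVA of PSQI-J change that uses neither baseline nor midway PSQI-J, although the sample size allows for about 43% loss

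*Protocol*

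**What the plan says.** Protocol section 10, 1) names the outcome as "Primary Endpoint: PSQI-J at 3 months post-educational intervention" and sets the population: "Analysis of the primary endpoint will be performed using the Full Analysis Set (FAS"). It then gives the method: "The change in PSQI-J for each group will be calculated, and between-group comparisons will be performed at a 5% significance level (two-tailed"). The model is an ANCOVA whose only named covariates are age and disease stage. A per-protocol repeat is secondary. Baseline PSQI-J is not among the covariates.

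Section 8 (1) schedules the score three times: "Assessment timepoints were at participant registration, the second intervention session, and study completion". Section 9 puts completion about 8 weeks after the second session. Table 1 marks PSQI-J as required at registration, second intervention and completion, and as optional at cancellation.

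Section 5, on the rationale for sample size, says that "a higher dropout rate than usual is expected" and raises enrolment from 17 to 30 per group. It gives no dropout rate. The protocol does not define the FAS or state a rule for missing scores. It also does not say that patients without a final score are excluded.

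**The concern.** A change to 3 months cannot be calculated for someone who has no 3-month score. Naming the FAS does not supply one. Unless scores are imputed, such a patient leaves the primary comparison, even if the midway PSQI-J was recorded.

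Two things are at stake.

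- **Precision.** Baseline PSQI-J, and the midway score for patients lost after it, carry information on the 3-month score. The stated model uses the first only through subtraction and the second not at all.
- **Bias.** A larger sample protects power but does not make completers comparable between arms. Section 5 attributes the expected loss to difficulty with computers and video conferencing. That burden is heavier in the intervention arm, which has two video education sessions (section 7) and calls of about 60 minutes against 30 (section 14, 3)). Loss could therefore differ by arm.

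**Working it through.** **Inputs from the protocol**
- Two-sided 5% test, 80% power, 17 per group before the dropout allowance, 30 per group enrolled. The list of target sizes gives 40 for control, but the total of 60 and the rationale both imply 30, which is used here.
- Effect: "we assumed a mean reduction of 5.0 points in the PSQI-J score at 3 months in the intervention group". It is treated here as the between-group difference.

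**Inputs assumed**
- SD 5. No SD is readable (a figure is not shown).
- PSQI-J correlations of 0.6 (baseline–midway), 0.5 (baseline–final) and 0.7 (midway–final).

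**1. The plan's own figure.** The normal formula n = 2(1.96 + 0.84)² × SD² / 5² gives 15.7, rounded up to 16, at SD 5. It gives 17 for SD about 5.05 to 5.20. The exact t-test calculation gives 17 for SD about 4.89 to 5.04. So 17 is consistent with an SD near 5, but it can only be solved backwards, not strictly reproduced.

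**2. Implied loss.** 17 / (1 − d) = 30 gives d = 1 − 17/30 = 43.3%, or 13 of 30 per arm. With 17 completers per arm, power for 5 points at SD 5 is 0.807. The allowance therefore covers power.

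**3. Baseline covariate.** With correlation ρ between baseline and final score, the variance of the change is 2(1 − ρ)SD². The residual variance after baseline adjustment is (1 − ρ²)SD². The ratio is (1 + ρ)/2, which is 0.75 at ρ = 0.5, 0.65 at ρ = 0.3 and 0.85 at ρ = 0.7. It is below 1 for any ρ < 1.

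**4. Precision under random loss.** Simulation with 30 per arm, 43% lost at random after the midway visit and 3,000 replicates. The midway analysis regresses the final score on arm, baseline and midway score in completers, predicts the missing finals, then adjusts for baseline.

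| Analysis | SD of estimate |
|---|---|
| Completers, change | 1.74 |
| Completers, with baseline | 1.53 |
| Using midway score and baseline | 1.42 |

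Variance ratios: (1.53/1.74)² = 0.77 for adding baseline, (1.42/1.53)² = 0.86 for then adding the midway score, and (1.42/1.74)² = 0.67 for both. Age and stage were not simulated.

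**5. When the loss occurs.** In a separate run on the same assumptions, baseline ANCOVA against the midway-score model gave 1.52 and 1.40 with all loss after the midway visit. It gave 1.54 and 1.49 with 30 of the 43 percentage points before it, and 1.55 and 1.55 with all loss before it.

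**6. Bias.** Loss was simulated by a logistic rule in which the odds of leaving rise by a factor of e for each 5-point worsening from baseline to midway. Large-sample means follow; negative values favour education.

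| Scenario (loss, intervention / control) | True effect | Change | With baseline | Midway used |
|---|---|---|---|---|
| Random, 43% / 43% | 0 | 0.01 | 0.00 | 0.01 |
| Same rule in both arms, 44% / 44% | 0 | 0.00 | 0.00 | 0.00 |
| Rule in intervention arm only, 44% / 20% | 0 | −1.15 | −0.78 | −0.01 |
| Rule in intervention arm only, 33% / 15% | 0 | −0.82 | −0.55 | 0.02 |
| Rule in intervention arm only, 44% / 43% | 0 | −1.13 | −0.77 | 0.00 |
| Rule in intervention arm only, 46% / 20% | −5 | −6.18 | −5.80 | −5.01 |
| Same rule in both arms, 37% / 44% | −5 | −4.83 | −4.89 | −5.01 |

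Bias needs a dropout mechanism that differs by arm; different rates are not required. The last row shows a small bias against education, because a real effect moves the intervention arm along the same rule.

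**The case against.** The strongest reply is that the protocol does not prescribe a completers' analysis. It names the FAS, and ANCOVA can be combined with imputation that uses the midway score. The FAS definition and missing-data rules commonly sit in a statistical analysis plan, which is not at hand. PSQI-J may also be collected at cancellation. This stands: a reader might infer that patients without a final score are dropped, but the protocol does not say so, and its silence on imputation is not a fault.

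A reader might also infer that the result will be biased in favour of education. The protocol does not support that. It attributes dropout to device difficulty, not to failure to improve, and both arms use video calls. The bias above comes from one chosen arm-specific rule. Loss from device trouble may also fall before the midway score exists, where that score cannot help (step 5).

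Finally, ANCOVA of change at the named time point is a standard choice for a 60-patient trial. That is so. But the choice of covariates and of a single time point is stated in the protocol, not left open, and it discards data that the protocol requires to be collected.

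**Conclusion.** The point holds as a weakness of the stated method, not as a demonstrated bias. The protocol fixes a one-time-point analysis of change without baseline PSQI-J or the midway score, in a trial sized for about 43% loss.

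Under the assumed SD and correlations, with random loss after the midway visit, adding baseline cuts the variance of the estimate by about 23%. Adding the midway score as well brings the reduction to about 33%. The baseline gain does not depend on when patients leave. The midway gain shrinks to nothing if all loss comes first.

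If missing scores are not imputed and loss depends on midway response only in the intervention arm, the planned comparison is off by about 0.8 to 1.2 points in favour of education. Under random loss, or under the same rule in both arms with no true effect, it is off by about zero. The 43% is implied by 17 and 30 and is not stated as a rate. At the planned effect and SD 5, power is already covered, so the case rests on precision and on protection against arm-specific loss.

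**What to change.** Make the primary analysis a likelihood-based repeated-measures model of the midway and 3-month PSQI-J, with baseline PSQI-J, age, disease stage and group by time. The test is the 3-month group difference. ANCOVA with baseline PSQI-J and multiple imputation that uses the midway score would serve the same end.

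State the week at which controls complete the midway PSQI-J, matched to the intervention arm. Section 8 (1) ties that score to the second session, and section 6 describes no such session for controls. Without a set week, neither version of the fix compares like with like.

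Keep the planned ANCOVA as a sensitivity analysis, and add one for non-random dropout. Make the change before outcome data are seen by group.

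The cost is protocol wording, a little more analysis work and reliable midway collection in controls. The downsides are reliance on missing-at-random and little gain from the midway score if most patients leave before it. The baseline covariate is worth adding in either case.

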#### 4. Allocation Method

Stratified block allocation will be used, with gender (male, female) and severity classification (Grade 1, 2, 3, 4) as allocation factors. Allocation of subjects to each treatment group will be performed by [name] at the Department of Basic Nursing Science, Kumamoto University Graduate School.

Following a pre-generated random allocation table, subjects will be sequentially assigned to treatment groups in the order of case registration. A registration confirmation document listing the subject registration number and group name will be issued. The allocation table will be retained by the person responsible for allocation and will not be disclosed to the Principal Investigator or Co-Investigators.

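### The primary ANCOVA of PSQI-J change leaves out baseline PSQI-J, which is collected anyway, and so gives up precision

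*Protocol*

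**What the plan says.** The protocol's Analysis Methods (III.10, Analysis of Primary Endpoint) name the endpoint as "Primary Endpoint: PSQI-J at 3 months post-educational intervention". They go on: "The change in PSQI-J for each group will be calculated", with the groups compared at the two-sided 5% level by "covariance analysis adjusted for the background factors of age and disease stage classification". These are the only covariates named, and no other section adds one.

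Baseline PSQI-J will be available. Under Primary Evaluation Item (III.8): "Assessment timepoints were at participant registration, the second intervention session, and study completion". The enrollment list in III.9 includes "Sleep Quality: PSQI-J, JESS", and Table 1 marks PSQI as required at registration.

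The design does not balance it. Under Allocation Method (III.4): "Stratified block allocation will be used, with gender (male, female) and severity classification (Grade 1, 2, 3, 4) as allocation factors".

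On size, the Rationale for Sample Size (III.5) states that "we assumed a mean reduction of 5.0 points in the PSQI-J score at 3 months in the intervention group", derives 17 per group for 80% power, and raises enrollment to 30 per group because "a higher dropout rate than usual is expected". It gives no dropout rate, and no SD can be read in the text.

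**The concern.** The baseline value of the outcome is usually the strongest single predictor of its later value, and here it is omitted while two weaker background factors are kept. Analysing change uses baseline, but only by fixing its slope at 1. When the true slope is below 1, as it is under equal variances and imperfect correlation, the change score carries avoidable noise. Part of any chance difference between the arms at baseline also stays in the estimate.

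Power in the one test that decides the trial is at stake. The protocol itself points to two conditions in which that power could run short. It expects heavy dropout. Its 5.0 points is a fall within the intervention group, so any improvement among controls, who receive a pamphlet and a technique check by video (III.6), makes the between-group effect smaller than 5.

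**Working it through.** **Inputs from the protocol.** Effect 5.0 points, two-sided 5%, power 80%, 17 per group required, 30 per group enrolled (III.5); covariates age and four-level stage (III.10, III.4). The Target Sample Size list shows 40 controls beside a total of 60; 30 per arm, as in the rationale, is used here.

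**Inputs assumed.** Equal PSQI-J variance at baseline and 3 months; ρ of 0.3, 0.5 or 0.7; age and stage explain no outcome variance and cost only degrees of freedom.

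**Step 1, the protocol's 17 per group.** Without a readable SD this cannot be reproduced directly, only back-solved. A two-sample t-test with 17 per group, 5 points and 80% power (32 df) needs an SD of 5.05. The normal approximation returns 17 for SDs of about 5.05 to 5.20. The figure is consistent with an SD of about 5.

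**Step 2, variance ratio.** With score variance σ²:

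- change score without baseline: 2σ²(1−ρ)
- with baseline in the model: σ²(1−ρ²)
- ratio: (1−ρ²)/[2(1−ρ)] = (1+ρ)/2

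| ρ | Variance ratio | Fall in SE | Per-arm n with baseline matching 30 without (30 × ratio) |
|---|---|---|---|
| 0.3 | 0.65 | 19% | 19.5 |
| 0.5 | 0.75 | 13% | 22.5 |
| 0.7 | 0.85 | 8% | 25.5 |
| 0.8 | 0.90 | 5% | 27.0 |

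A simulation at 17 per arm, with age and stage in both models, gave ratios of 0.68, 0.76 and 0.86 at ρ = 0.3, 0.5 and 0.7, close to theory.

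**Step 3, power.** Noncentral t with noncentrality δ/(s√(2/n)). As planned, s = 5.05 and df = 2n−6 (intercept, treatment, age, three stage terms). With baseline, s = 5.05√[(1+ρ)/2] and df = 2n−7.

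| Effect, n per arm | Planned | ρ 0.3 | ρ 0.5 | ρ 0.7 |
|---|---|---|---|---|
| 5 points, 30 | 96.5% | 99.7% | 99.2% | 98.3% |
| 5 points, 17 | 79.6% | 93.2% | 89.5% | 85.6% |
| 4 points, 30 | 85.4% | 96.2% | 93.6% | 90.5% |
| 3 points, 30 | 61.9% | 80.1% | 74.2% | 68.9% |

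Simulation (10,000 trials per cell, stratified blocks of 4; block size and stratum mix assumed) gave slightly lower values with the same pattern. For 5 points at 17 per arm it gave about 77% against 91%/87%/82%; for 3 points at 30 per arm, 60–61% against 79%/72%/66%. Type I error was 5.0–5.3% as planned and 4.9–5.4% with baseline.

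**Step 4, if 5.05 is the SD of the score.** The change SD is then 5.05√[2(1−ρ)], and power at ρ = 0.3/0.5/0.7 becomes:

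- 5 points, 17 per arm: 65%/80%/95% planned against 83%/90%/97% with baseline
- 3 points, 30 per arm: 48%/62%/83% planned against 66%/74%/89% with baseline

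The two readings coincide at ρ = 0.5. A change SD of 5.05 at ρ = 0.7 implies a score SD of 5.05/√0.6 = 6.52, too wide to be plausible on a 0–21 scale, so that column of Step 3 is the least reliable.

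**Step 5, what chance imbalance looks like.** This illustrates the variance already counted in Step 2 and is not a further loss. With a PSQI-J SD of 3, 4 or 5 (assumed) and 30 per arm, the SE of the baseline difference is SD × √(2/30) = 0.77, 1.03 or 1.29 points. The probability that it exceeds 1 point in either direction is 20%, 33% or 44%. The planned estimate retains (1−ρ) of the difference. For a difference of one standard error, that is from 0.3 × 0.77 = 0.23 to 0.7 × 1.29 = 0.90 points.

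**The case against.** The strongest reply is that nothing here is an error. The planned comparison is valid, the change score already uses baseline, and at the protocol's own design point (5 points, 30 per arm) power is about 96% before any change. The larger gains need 17 evaluable per arm, which is a calculated requirement and not a forecast and would mean 1 − 17/30 = 43% dropout, or a 3-point effect, a figure the protocol never mentions. ρ and the SD are both unknown. At higher ρ the gain shrinks: for 5 points at 17 per arm, power with baseline is 83.5% at ρ = 0.8 and 81.5% at ρ = 0.9, against 79.6% as planned.

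All of that stands as a limit on the size. It does not remove the point. The variance ratio is below 1 for every ρ below 1, and under none of the assumptions examined does adding baseline lower power. Nor can the matter be treated as a detail left to a statistical analysis plan. The protocol names its covariates, so a plan that added baseline would depart from the stated primary model.

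Gender is also an allocation factor absent from the model. How much precision it would add depends on how much outcome variance it explains, which the protocol does not say. It is a consistency point only.

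**Conclusion.** The point holds as a loss of precision, not as bias or a faulty test. Under equal variances, omitting baseline PSQI-J inflates the variance of the primary estimate by a factor of 2/(1+ρ). Equivalently, including it would cut that variance by 15–35% for ρ from 0.7 down to 0.3, and by 10% at ρ = 0.8.

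The practical consequence is small if the between-group effect is really 5 points and nearly all 30 per arm are evaluable. It becomes material if dropout is heavy or the true effect is nearer 3 points. The variance ratio rests on equal variances and the assumed ρ. The power figures rest in addition on the back-solved SD and on its being the SD of change. The change should be made because it improves the decisive test at almost no cost, but the trial is not invalid without it.

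**What to change.** In III.10, Analysis of Primary Endpoint, specify the primary model as ANCOVA of PSQI-J change (or, equivalently for the treatment effect, the 3-month score) on treatment, baseline PSQI-J, age and disease stage. For consistency with III.4, gender can be added so that both allocation factors are in the model.

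The cost is one sentence and one degree of freedom, with a second for gender (about 0.1 percentage point of power). No visit, instrument or data item is added. The change should be made before outcome data are seen, so that a chance baseline imbalance does not later force a choice between adjusted and unadjusted results.

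### Sex is an allocation factor but is not in the primary ANCOVA; if sex predicts PSQI-J change, the primary test is somewhat conservative, and adding sex costs one degree of freedom

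*Protocol*

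**What the plan says.** Protocol III.4 (Allocation Method) describes stratified blocks "with gender (male, female) and severity classification (Grade 1, 2, 3, 4) as allocation factors". That makes 2 x 4 = 8 strata. The block size is not stated.

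Protocol III.10, 1) (Analysis of Primary Endpoint) compares the change in PSQI-J between groups in the FAS, two-sided at 5%, by "covariance analysis adjusted for the background factors of age and disease stage classification". The same analysis is repeated in the PPS. The section describes a test and mentions no confidence interval.

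Protocol III.9 (At the time of enrollment) lists gender among the background data, and allocation cannot proceed without it. No section adds sex to the primary model or explains its absence.

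**The concern.** If disease stage classification means the severity grade used at allocation, one stratification factor enters the model and the other does not. Stratified blocks make the arms similar on sex, so most of the variance that sex explains is removed from the true sampling variance of the treatment estimate. A model without sex still counts that variance as residual error. Its standard error is then too large, its test rejects too rarely under the null, and some power is lost. The trial plans only 60 participants and expects more dropout than usual, so precision matters.

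A statistical analysis plan may exist, but this is not a point the protocol leaves open. It names the covariates, and a later plan that added sex would depart from it.

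**Working it through.** **1. The plan's own figure.** Protocol III.5 states "we assumed a mean reduction of 5.0 points in the PSQI-J score at 3 months in the intervention group", with two-sided 5% and 80% power, and that "the required sample size was calculated to be 17 participants per group". No SD is readable in the text (a figure is not shown), so it can only be back-solved. The noncentral t power at a standardised difference of 1.0 is 0.781 with 16 per group and 0.807 with 17. The normal approximation gives 16 per group at SD 5.0 and 17 at SD 5.1-5.2. So 17 per group corresponds to an SD of about 5 points and an effect of about 1.0 SD. This is a consistency check, not an independent reproduction.

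**2. Formula.** Let p be the proportion of women and g the difference between the sexes in PSQI-J change, in residual SDs. With the arms balanced on sex, the ratio of the standard error without sex to that with sex is

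sqrt(1 + p(1 - p)g²).

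Example: p = 0.2 and g = 0.5 give sqrt(1 + 0.16 x 0.25) = sqrt(1.04) = 1.020.

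**3. Simulation of interval width and type I error.** From the protocol: 8 strata, N = 60, and covariates age and grade. Assumed: blocks of 4, grade mix 25/40/25/10%, residual SD 5, and no loss. There were 8,000 null trials per row. The Monte Carlo standard error of a 5% rejection rate is sqrt(0.05 x 0.95 / 8000) = 0.0024.

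| Women | g | 95% half-width without sex | with sex | ratio | formula | type I without sex | with sex |
|---|---|---|---|---|---|---|---|
| 10% | 0 | 2.610 | 2.624 | 0.995 | 1.000 | 0.050 | 0.050 |
| 10% | 0.5 | 2.638 | 2.622 | 1.006 | 1.011 | 0.050 | 0.052 |
| 10% | 1.0 | 2.729 | 2.625 | 1.040 | 1.044 | 0.044 | 0.049 |
| 20% | 0 | 2.613 | 2.619 | 0.997 | 1.000 | 0.046 | 0.048 |
| 20% | 0.5 | 2.667 | 2.623 | 1.017 | 1.020 | 0.042 | 0.047 |
| 20% | 1.0 | 2.820 | 2.623 | 1.075 | 1.077 | 0.040 | 0.051 |
| 50% | 0 | 2.615 | 2.620 | 0.998 | 1.000 | 0.047 | 0.047 |
| 50% | 0.5 | 2.693 | 2.617 | 1.029 | 1.031 | 0.044 | 0.050 |
| 50% | 1.0 | 2.927 | 2.619 | 1.118 | 1.118 | 0.032 | 0.053 |

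At g = 1.0 without sex, the model's mean standard error exceeds the true one: 1.41 against 1.33 at 20% women, and 1.46 against 1.33 at 50%.

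**4. Power.** Assumed: an effect of 1.0 SD (step 1), 60 randomised in blocks of 4, 20% random loss, and 10-30% women. If sex explains a share R² of the variance of change, the sex difference this requires is g = sqrt(R² / [(1 - R²)p(1 - p)]). Points are g times an SD of 5.

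| R² | g at 30% to 10% women | In PSQI-J points | Power gained by adding sex |
|---|---|---|---|
| 0 | 0 | 0 | none |
| 5% | 0.50 to 0.76 | 2.5 to 3.8 | about 1 point |
| 10% | 0.73 to 1.11 | 3.6 to 5.6 | about 1-2 points |
| 15% | 0.92 to 1.40 | 4.6 to 7.0 | about 2-3 points |

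Power without sex is about 90-92% in all of these.

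**The case against.** The strongest objection is that the effect is conditional and probably small. A reader might infer that the primary interval is too wide as the plan stands. The protocol does not support that: it gives no relation between sex and PSQI-J change, and with no relation the interval without sex is, if anything, marginally narrower (ratio 0.995-0.998). The larger scenarios need a difference between women and men of about the size of the whole assumed treatment effect. This objection stands and limits the point to a modest one.

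A reader might also infer a larger power loss. At an effect of 0.82 SD with the same 20% loss, adding sex gains about 2, 4 and 5 points when sex explains 5%, 10% and 15%. But the protocol does not state that effect; its own figures imply about 1.0 SD. Loss heavy enough to leave 17 per group would bring power back towards 80%, and that case was not simulated.

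Two further inferences fail. Sex is not guaranteed to be equal between the arms: eight strata among 60 people leave incomplete blocks, and dropout can disturb the balance further. Adjusting for age is not a defect either, since a covariate need not be an allocation factor.

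The mismatch between the two sections is not answered by any of this. Nor is the direction of the effect, or the absence of any stated reason for omitting sex.

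**Conclusion.** The point holds as a precision and alignment improvement. The model leaves out a factor that the trial randomises by. If that factor is prognostic, the test is conservative: about 0-3% in interval width for a sex difference of up to 0.5 residual SD, and about 4-12% near 1 SD. Near 1 SD the type I error is about 4% at 20% women and about 3% at 50%. The power at stake is about 1-3 points under the 1.0 SD effect and the assumed loss.

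A reader might see a threat to validity here. There is none: omitting sex introduces no bias and does not raise the type I error above 5%. The sample size of 17 per group is also unaffected, because it reproduces as an unadjusted comparison.

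The mismatch itself is certain, provided that disease stage classification is the severity grade. The size rests on assumed values for the sex effect, sex mix, grade mix, block size and loss. It also rests on "we increased the target enrollment to 30 participants per group, for a total of 60 participants"; the Target Sample Size list gives 40 controls, which conflicts with its own total of 60 and needs separate correction.

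**What to change.** In Protocol III.10, 1), state the primary model as an ANCOVA of the change in PSQI-J with treatment group and, as covariates, both allocation factors (sex; severity grade 1-4) and age. Use the same term for severity as in III.4, so that it is clear that the allocation grade is meant. Apply the same covariates in the PPS repeat.

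The cost is one line of text and one degree of freedom, with no new data. If sex turns out to be unrelated to the outcome, the price is negligible (half-width 2.62 against 2.61 at 20% women). Making the change before the data are analysed also avoids a later dispute about the choice of covariates.
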